8.3 Statistical Analysis Plan

8.3.1 Analysis of the Conduct of the Trial

Enrollment, major protocol violations, and discontinuations for the trial will be summarized using a CONSORT diagram.

8.3.2 Analysis of Patient Characteristics

Demographic and baseline characteristics, such as age, race, BSA, duration of pancreatic cancer, site(s) of metastatic disease, prior cancer treatment, and baseline ECOG performance status will be summarized using means (\pm standard error) or medians (range) for continuous variables and proportions for categorical variables.

8.3.3 Analysis of Pembrolizumab and Paricalcitol Administration

Pembrolizumab + Paricalcitol (or placebo) dose administration will be listed and dose modifications will be flagged. Mean and standard deviations will be used to summarize the average dose received.

8.3.4 Analysis of Primary Endpoint - Disease progression at 6 months

All patients that receive trial treatment will be included in the analysis to determine the percentage of patients progressing by RECIST 1.1 criteria at 6 months when maintained on a combination regimen of paricalcitol plus pembrolizumab versus pembrolizumab alone. The 6-month time-point will be defined as 6 months (180 days) from the initial treatment (cycle 1/day 1). Statistical analysis will compare the proportion progression free at 6 months using a one-sided test of binomial proportions (equivalent to a Pearson's chi-squared test). If the assumptions of the Pearson's chi-squared test are not met, we will analyze the data using Barnard's exact unconditional test of equality, as implemented in StatXact²⁰

8.3.5 Analysis of Secondary Endpoints

8.3.5.1 Analysis of Toxicities

All adverse events occurring on or after Cycle 1/day 1 will be summarized by body systems and per grade according to NCI-CTCAE Version 4. Additionally, all serious adverse events and events of clinical interest (ECI) as defined in section 6.2.3.2 will be listed separately and tabulated. All patients who receive any amount of trial treatment will be included in the analysis.

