1.5 Paricalcitol (Zemplar®)

Refer to Appendix 2- Package Insert for Paricalcitol for complete information.

Paricalcitol is a vitamin D analog used for the prevention and treatment of secondary hyperparathyroidism. Excessive amounts of vitamin D compounds including paricalcitol can cause over suppression of the parathyroid hormone, hypercalcemia, hypercalciuria, hyperphosphatemia and adynamic bone disease.

Paricalcitol should not be given to patients with evidence of vitamin D toxicity, hypercalcemia, or hypersensitivity to any ingredient in this product.

The most common side effects of treatment with paricalcitol are diarrhea, nasopharyngitis, dizziness, vomiting, hypertension, hypersensitivity, nausea and edema.

Taste perversion, such as metallic taste, and allergic reactions, such as rash, urticaria and pruritus rarely have been reported.

Risks associated with treatment with paricalcitol include: Symptoms of elevated calcium levels e.g. feeling tired, difficulty in thinking clearly, loss of appetite, nausea, vomiting, constipation, increased thirst, increased urination and weight loss. Prescription based doses of vitamin D should be withheld during treatment with paricalcitol.

The effects of paricalcitol on unborn fetus and possible transmission through breast milk have not been fully established. Patients on paricalcitol should avoid pregnancy and should not breast feed.

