4.1.1 Inclusion Criteria

Patients must meet the following criteria in order to be eligible for participation in the trial:

1. Be willing and able to provide written informed consent for the trial.
2. Be ≥ 18 years of age on day of signing informed consent.
3. Histologically or cytologically confirmed pancreatic adenocarcinoma with metastasis, who had obtained a best response of at least stable disease (SD) or a partial response (PR) for a period of 2 months with no further shrinkage of $\geq 30\%$ on scan on their first line of chemotherapy for their advanced metastatic disease.
Note: *Patients that have had prior chemotherapy as adjuvant or neoadjuvant therapy are permitted.*
4. Have a performance status of 0 or 1 on the ECOG performance scale.
5. Able to submit an archival tumor specimen (primary or metastatic site) and a discussion is documented with trial investigator at screening that patient will consider providing tissue from a newly obtained core or excisional biopsy of a tumor lesion at baseline and a second biopsy 9 weeks after starting trial treatment, unless tumor is considered inaccessible or biopsy is otherwise considered not in the patients best interest. *Participation in this trial is not contingent on patient consenting to optional tumor biopsies.*
6. Demonstrate adequate organ function as defined below in Table 2. AND serum corrected calcium value must be \leq Institutional ULN and ≥ 8.0 mg/dL, and phosphorus levels must be \leq Institutional ULN and ≥ 2.5 mg/dL.

Table 2. Adequate Organ Function Laboratory Values

| System | Laboratory Value |
|---|--|
| Hematological | |
| Absolute neutrophil count (ANC) | $\geq 1500/\mu\text{L}$ |
| Platelets | $\geq 100\ 000/\mu\text{L}$ |
| Hemoglobin | ≥ 9.0 g/dL or ≥ 5.6 mmol/L ^a |
| Renal | |
| Creatinine OR Measured or calculated ^b creatinine clearance (GFR can also be used in place of creatinine or CrCl) | $\leq 1.5 \times \text{ULN}$ OR ≥ 30 mL/min for participant with creatinine levels $> 1.5 \times$ institutional ULN |
| Hepatic | |
| Total bilirubin | $\leq 1.5 \times \text{ULN}$ OR direct bilirubin $\leq \text{ULN}$ for participants with total bilirubin levels $> 1.5 \times \text{ULN}$ |

| | |
|---|---|
| AST (SGOT) and ALT (SGPT) | $\leq 2.5 \times \text{ULN}$ ($\leq 5 \times \text{ULN}$ for participants with liver metastases) |
| Coagulation | |

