6.1.3 Laboratory Procedures/Assessments

Safety laboratory tests for hematology, chemistry, and urinalysis (as detailed in Table 9) will be performed by the local laboratory for each investigational site at screening, baseline and throughout the trial treatment period. Serum vitamin D levels will be performed at screening. HBsAg and HCV RNA (qualitative) will be performed at screening if not performed within the last 3 months. Thyroid and Parathyroid function (T3, FT4 TSH, and PTH) will be performed as part of screening and every other cycle during the trial treatment period.

Table 9. Laboratory Tests – performed locally

| Hematology | Chemistry | Urinalysis | Other |
|------------------------------|----------------------------------|---|--|
| Hematocrit | Albumin | Blood | Serum β -human chorionic gonadotropin† |
| Hemoglobin | Alkaline phosphatase | Glucose | PT (INR) |
| Platelet count | Alanine aminotransferase (ALT) | Protein | aPTT |
| WBC (total and differential) | Aspartate aminotransferase (AST) | Specific gravity | Thyroid stimulating hormone (TSH) |
| Red Blood Cell Count | Lactate dehydrogenase (LDH) | Microscopic exam (If abnormal results are noted) | Total triiodothyronine (T3) |
| Absolute Neutrophil Count | Carbon Dioxide ‡ | | Free thyroxine (T4) |
| Absolute Lymphocyte Count | (CO ₂ or bicarbonate) | | PTH (parathyroid hormone) |
| | Uric Acid | | Serum vitamin D (25- |

| Hematology | Chemistry | Urinalysis | Other |
|--|--|------------|---------------------|
| | | | hydroxy vitamin D) |
| | Calcium | | HBsAG |
| | Chloride | | HCV RNA qualitative |
| | Glucose | | |
| | Phosphorus | | |
| | Potassium | | |
| | Sodium | | |
| | Magnesium | | |
| | Total Bilirubin | | |
| | Direct Bilirubin (If total bilirubin is elevated above the upper limit of normal) | | |
| | Total protein | | |
| | Blood Urea Nitrogen | | |
| | Creatinine | | |
| † Perform on women of childbearing potential (WOCBP) only. | | | |
| ‡ If considered standard of care in your region. | | | |

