Day 3, 5, 8, 10, 12, 15, 17, and 19 (\pm 1 day) of each cycle

- Vital signs
- AEs using the NCI CTCAE (Appendix 3)
- Concomitant medication notation
- **Day 8 and 15 of each cycle only:** Directed physical exam, including weight
- **Day 8 and 15 of each cycle only:** ECOG Performance Status
- **Day 8 and 15 of each cycle only:** Hematology: CBC with differential and platelet count - results must be reviewed prior to paricalcitol administration
- **Day 8 and 15 of each cycle only:** Serum chemistries (refer to Table 9) - results must be reviewed prior to paricalcitol administration
- **Day 8 and 15 of each cycle only:** Patient to complete the Patient Personalized Clinical Benefit (PPCB) App (Appendix 6)
- **Day 19 Only:** Provide Fecal Swab collection kit and review instructions with patient for return of sample on Day 1 on next treatment cycle
- Paricalcitol administration

Week 9 (+/- 1 week)

- Optional repeat biopsy refer to Section 6.1.2.8
- Central Lab Blood Sample, 2 X 10 mL vials refer to Section 6.1.2.7

End of 3 treatment cycles (every 9 ± 1 weeks) until disease progression or end of trial, whichever comes first

- CT/MRI scan to evaluate disease status (using same imaging method as Baseline). Obtain De-identified dicomm encoded CT scan for central lab (Appendix 7).

Note: In order to more precisely determine time to progression, the investigator is encouraged to obtain radiological assessments and CA19-9 values earlier if there is a strong clinical suspicion of disease progression. In order to either confirm or refute the clinical impression.

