6.2 Assessing and Recording Adverse Events

An adverse event is defined as any untoward medical occurrence in a patient or clinical investigation patient administered a pharmaceutical product and which does not necessarily have to have a causal relationship with this treatment. An adverse event can therefore be any unfavorable and unintended sign (including an abnormal laboratory finding, for example), symptom, or disease temporally associated with the use of a medicinal product or protocol-specified procedure, whether or not considered related to the medicinal product or protocol-specified procedure. Any worsening (i.e., any clinically significant adverse change in frequency and/or intensity) of a preexisting condition that is temporally associated with the use of the pembrolizumab and /or paricalcitol, is also an adverse event.

Adverse events may occur during the course of the use of pembrolizumab and/or paricalcitol in clinical trials, or as prescribed in clinical practice, from overdose (whether accidental or intentional), from abuse and from withdrawal.

Progression of the cancer under study (pancreatic cancer) is not considered an adverse event.

All adverse events that occur after the consent form is signed but before treatment allocation/randomization must be reported by the investigator if they cause the patient to be excluded from the trial, or are the result of a protocol-specified intervention, including but not limited to washout or discontinuation of usual therapy, diet, placebo treatment or a procedure.

From the time of treatment allocation/randomization through 30 days following cessation of treatment, all adverse events must be reported by the investigator. Such events will be recorded at each examination on the Adverse Event case report forms/worksheets. The reporting timeframe for adverse events meeting any serious criteria is described in section 6.2.3.1. The investigator will make every attempt to follow all patients with non-serious adverse events for outcome.

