7 STATISTICAL METHODOLOGY

7.1 STATISTICAL PROCEDURES

Primary outcome: Progression-free survival

The proportion of patients in each arm who are progression-free at 6-months will be compared using a one-sided test of binomial proportions (equivalent to a Pearson's chi-squared test). If the assumptions of the Pearson's chi-squared test are not met, Barnard's exact unconditional test of equality will be used, as implemented in StatXact.

Patients unevaluable for progression at 6-months due to a non-progression related event will be excluded from analysis.

Statistical comparison of progression-free survival between the two treatment arms will be performed using a log-rank test, with estimation of the hazards ratio using a Cox proportional hazards model. A sensitivity analysis will include patients with an outcome of death due to another cause (other than progressive disease), which will be considered a competing event for progression. Analysis will be performed using the Fine and Gray (1999) approach.

Secondary outcome 1: Toxicity

All adverse events (AE) occurring on or after C1/D1 will be summarized by body systems and per grade according to NCI-CTCAE Version 4. Additionally, all serious adverse events (SAE) and events of clinical interest (ECI) will be listed separately and tabulated. ECIs for this trial include an overdose of pembrolizumab and an elevated AST or ALT lab value, as defined in section 6.2.3.2 of the protocol. All patients who receive any amount of trial treatment will be included in the analysis. The proportion of patients in each arm with toxicity will be compared using a chi-squared test or Barnard's exact unconditional test of equality as outlined above.

Secondary outcome 2: Overall survival

Overall survival will be calculated for each arm using a Kaplan-Meier estimate. Statistical comparison of overall survival between the two treatment arms will be performed using a log-rank test, with estimation of the hazards ratio using a Cox proportional hazards model. Patients with an outcome of death due to another cause (other than progressive disease) will be considered a competing event for death. Analysis will be performed using the Fine and Gray (1999) approach.

Exploratory outcome 1: RECIST 1.1 versus iRECIST

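### Calcium, phosphorus and PTH are measured throughout treatment but have no planned by-arm summary, so changes not recorded as adverse events drop out of the toxicity comparison

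*Protocol*

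**What the plan says.** **Named risk.** Protocol 1.5 says that excessive amounts of vitamin D compounds, paricalcitol among them, "can cause over suppression of the parathyroid hormone, hypercalcemia, hypercalciuria, hyperphosphatemia and adynamic bone disease".

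**Objective.** Toxicity of the combination against pembrolizumab alone is the first secondary objective (protocol 3.2, SAP 3). Both arms receive pembrolizumab; the randomised contrast is paricalcitol against placebo (protocol 8.1).

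**What is measured.** The chemistry panel in protocol Table 9 includes calcium, phosphorus and albumin. Protocol 6.1.7.2 schedules it on Day 1 of each cycle and again on Days 8 and 15: "Serum chemistries (refer to Table 9) - results must be reviewed prior to paricalcitol administration". On thyroid and parathyroid function, protocol 6.1.3 ends: "PTH) will be performed as part of screening and every other cycle during the trial treatment period".

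**What is analysed.** Protocol 8.3.5.1: "All adverse events occurring on or after Cycle 1/day 1 will be summarized by body systems and per grade according to NCI-CTCAE Version 4". SAEs and events of clinical interest are listed and tabulated as well. SAP 7.1 repeats this and adds: "The proportion of patients in each arm with toxicity will be compared using a chi-squared test", or Barnard's exact test. Protocol 6.2.3.2 defines two events of clinical interest, a pembrolizumab overdose and a liver-test pattern.

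**What counts as an adverse event.** The definition in protocol 6.2 extends to "any unfavorable and unintended sign (including an abnormal laboratory finding, for example".

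**Calcium basis.** Inclusion criterion 6 reads "serum corrected calcium value must be" within stated limits. Table 9 lists calcium and albumin as separate items and gives no correction formula.

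**The concern.** The laboratory measures tied to the named risks of the randomised drug are collected often, yet the analysis sections never use them as measurements. They reach a table only if an investigator writes the change up as an adverse event. No passage says when a calcium, phosphorus or PTH change must be recorded, and protocol 4.6.2 speaks of clinically significant hypercalcemia without defining it. Recording therefore rests on individual judgement across up to 7 centers (protocol 4.1). The SAP compares patients with toxicity without saying whether a laboratory abnormality is enough to count.

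At stake is the completeness of secondary objective 1. The report could describe toxicity as similar in the two arms while the trial's own laboratory data, never summarised, show a difference.

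**Working it through.** No figure in the plan rests on this point, so there is none to reproduce. The check has four steps.

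**1. Collection against analysis** (protocol 6.1.3, 6.1.7.2, Table 7 footnote i, 8.3.5.1; SAP 7.1)

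| Measure | Scheduled | Planned by-arm summary of values | Other route into a table |
|---|---|---|---|
| Calcium | Days 1, 8, 15 of each cycle | None | Only if recorded as an AE or SAE |
| Phosphorus | Days 1, 8, 15 of each cycle | None | Only if recorded as an AE or SAE |
| PTH | Screening, then before cycles 3, 5, 7 and so on | None | Only if recorded as an AE or SAE |

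The proposed SAP Table 3 (grade 3 or higher) has rows for increased AST, ALT and alkaline phosphatase but none for these three. That does not show that no such event occurred, and a recorded event would still appear in the full adverse-event summary.

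**2. How much data is left unused**

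Cycle k starts on day 1 + 21(k − 1).

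- Treated to day 180: cycles 1 to 8 give 8 × 3 = 24 panels. Cycle 9 adds days 169 and 176, since day 183 falls outside. The total is 26 panels, the first of them at Cycle 1 Day 1 before dosing.
- PTH on treatment, before cycles 3, 5, 7 and 9: days 43, 85, 127 and 169, so 4 values.
- Stopping at the first 9-week scan: 3 cycles × 3 = 9 panels, and 1 PTH value (day 43).

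The larger counts are close to a maximum, because the protocol expects 92% of control patients to have progressed by 6 months. PTH is not in the end-of-treatment list (protocol 6.1.7.3, Table 8), so the last value is the last every-other-cycle draw.

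**3. How sensitive a comparison at 12 per arm is to one unrecorded patient** (hypothetical counts, no control events, two-sided test assumed)

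z = (x/12 − 0/12) / √[p̄(1 − p̄)(2/12)], with p̄ = x/24.

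- x = 4: p̄ = 0.1667, z = 0.3333/0.1521 = 2.19, p = 0.028.
- x = 3: p̄ = 0.1250, z = 0.2500/0.1350 = 1.85, p = 0.064.

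Expected events per arm are 4/2 = 2 and 3/2 = 1.5, so the SAP's fallback would probably apply. Barnard's test, which maximises over the common rate the probability of tables with |z| at least this large, gives 0.038 and 0.094. On either test, one patient whose change was not written up moves the result across 5%. This is an illustration, not a forecast.

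**4. Calcium basis, passages side by side**

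- Screening: corrected calcium is required (protocol 4.1.1, criterion 6).
- Day 1 of each cycle: chemistries are reviewed against the inclusion criteria (protocol 6.1.7.2), which brings in the corrected value.
- Days 8 and 15: the panel is reviewed before paricalcitol, with no mention of correction.
- Grading and hypercalcemia (protocol 6.2.4, 4.6.2): no mention of correction.

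The text is silent on part of the schedule. It does not state an uncorrected basis.

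**The case against.** The strongest reply is that the adverse-event route already does this work. The definition covers abnormal laboratory findings. For events not listed in CTCAE, Grade 1 in protocol 6.2.4 takes in asymptomatic findings seen only on testing. All adverse events from randomisation to 30 days after treatment must be reported, and chemistry results must be reviewed on Days 1, 8 and 15. SAP Table 3 lists anemia and raised liver enzymes among common events, so laboratory abnormalities were being recorded. The endpoint is incidence of toxicities, which an adverse-event analysis matches, and an independent medical monitor receives an unblinded report (protocol 9.8.2).

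Most of this stands. Recorded abnormalities are graded and tabulated, and nothing in the plan contradicts itself here. But the route still depends on someone deciding to record the change, and the monitor's report is oversight during conduct, not a planned analysis by arm.

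Two stronger readings are tempting and should not be drawn:

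- **That on-treatment calcium is uncorrected.** The documents do not say so. One Table 9 panel, with albumin, serves both screening and treatment, so its plain calcium label cannot show that later values are uncorrected; the Day 1 review points back to the corrected criterion.
- **That these are paricalcitol's main harm.** Protocol 1.5 does not rank them. It ties them to excessive amounts and lists other effects, such as diarrhea, nasopharyngitis and dizziness, as the most common.

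**Conclusion.** The gap is real but modest. Protocol 8.3 and the SAP contain no by-arm summary of calcium, phosphorus or PTH values, and neither event of clinical interest covers them. A change that no investigator records as an adverse event stays out of secondary objective 1. In scale, that is 9 to 26 scheduled panels and 1 to 4 on-treatment PTH values per patient for treatment lasting between 9 weeks and 180 days.

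How many changes would go unrecorded cannot be judged from the documents, so the conclusion is that the comparison can miss them, not that it will. Whether calcium is corrected on Days 8 and 15 or for grading remains unstated. CTCAE is given only by link, and I could read the footnotes of Table 7 but not its grid; a visit grid might specify correction but would not supply an analysis. This is a worthwhile, inexpensive addition and does not touch the primary endpoint or the sample size.

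**What to change.** Add to protocol 8.3.5.1 and SAP 7.1 descriptive summaries by arm of albumin-corrected calcium, phosphorus and PTH:

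- shift tables from baseline to the worst on-treatment value, against institutional limits;
- the number and percentage of patients ever above the limit (calcium, phosphorus) or below it (PTH);
- change from baseline at each scheduled PTH draw.

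For this analysis, name one correction formula and apply it to calcium at baseline and on treatment, using the albumin already on the panel. The tables would stand beside the adverse-event summary and not depend on which changes were recorded as events.

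The cost is a little programming, with no new test, visit or patient. The tables are descriptive: with 12 per arm, even 0 of 12 leaves a one-sided 95% upper bound of 1 − 0.05^(1/12) = 22%. No dosing rule, threshold for action or change to clinical review is proposed.

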8.3.5.2 Comparison of Overall Survival

Duration of survival will be defined as the time from initial treatment (cycle1/day1) until death. Overall survival will be estimated for each arm using a Kaplan-Meier estimate. Statistical comparison of overall survival between the two treatment arms will be performed using a log-rank test, with estimation of the hazards ratio using a Cox proportional hazards model.

8.3.5.3 Analysis of Tumor Mutational Landscape and Transcriptional Programs

The change in the biomarkers in the pre- versus 6-week biopsies will be estimated for each patient. A two-sample t test will be used to compare the continuous changes between the two treatment arms, assuming that the differences are normally distributed. If they are non-normal, a Wilcoxon Rank Sum Test will be used. A sensitivity analysis will use a linear regression model to compare the two treatment arms, adjusted for the baseline level.

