Two passes will be split evenly and processed for formalin-fixed paraffin (FFP) and optimal cutting temperature (OCT) embedding and samples will be centrally analyzed using existing technologies, such as immunohistochemistry, immunofluorescence, and RNA-in situ hybridization, as well as various new technologies as they become available to evaluate the following:

- Stromal/extracellular matrix content (e.g. collagen and hyaluronic acid)
- Quantity and quality of vascularization (e.g. CD31)
- Expression of pembrolizumab related targets (e.g. PD-1 and PD-L1)
- Presence/ distribution, and activation of key immune cell populations (e.g. cytotoxic T Cells, TAMs, MDSCs, and Tregs)
- Presence, distribution, and activation of other stromal cell populations, including fibroblasts (e.g. α SMA)

One pass will be immediately snap frozen for the following central analysis

- Analysis of bulk tumor RNA for VDR expression and VDR targets (e.g. CYP24A1)
- Analysis of bulk tumor RNA for Expression of VDR regulated inflammatory gene (e.g. IL6, CXCL1, CSF2, CXCLR)

Two passes will be immediately frozen in Bambanker™ freezing media for the following central analysis:

- Genomic analysis of T-cell receptor clonality by sequencing (a measure of intratumoral T cell response)

Bulk and single-cell analysis of mutational profiles, transcriptional profiles, and epigenetic states within tumors, including analysis of sorted tumor cell nuclei.

In the event that biopsy tissue becomes limiting for certain analyses, snap frozen and Bambanker™ frozen tissue may be used interchangeably where technically feasible.

Specific details for tumor tissue collection and handling will be provided to the investigative sites in the Trial Laboratory Manual.

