8.3.5.3 Analysis of Cellular VDR targets with PD1 Blockade

Analysis of the specified cellular VDR targets will be assessed using the change in the pre-versus 9-week biopsies. A two-sample t test or Wilcoxon Rank Sum Test, and a sensitivity analysis using linear regression will be performed as outlined previously.

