Comparison of the proportion of patients who are progression-free at 6 months using iRECIST will be performed using the same method as for the primary endpoint of RECIST 1.1. McNemar's test will be used to estimate the concordance between RECIST 1.1 and iRECIST.

7.2 MEASURES TO ADJUST FOR MULTIPLICITY, CONFOUNDERS, HETEROGENEITY, ETC.

Since all primary and secondary endpoints are pre-specified, there will be no adjustment for multiple comparisons. In the context of a randomized clinical trial, the two treatment arms are expected to be balanced with regard to potential confounders, therefore, adjustment is generally not necessary.

References:

Fine, J. P., and R. J. Gray. 1999. A proportional hazards model for the subdistribution of a competing risk. *Journal of the American Statistical Association* 94: 496–509.

Proposed Tables

Table 1. Characteristics of patients at baseline

Characteristic	Pembrolizumab n = x	Pembrolizumab + Paricalcitol n = x	Total n = x
Age, y			
Median			
Range			
Sex, n (%)			
Female			
Male			
Race/ethnicity, n (%)			
Asian			
Black			
White			
Hispanic			
Other			
Study site, n (%)			
HonorHealth Research Institute			
City of Hope			
Atlantic Health System			
Baylor Scott and White Research Institute			
University of Kansas Medical Center			
Medical College of Wisconsin			
Pancreatic tumor location, n (%)			
Head			
Body			
Tail			
Unknown			
Site of metastatic disease, n (%)			
Liver			
Lung			
Peritoneum			
No. of metastatic sites, n (%)			
1			
2			
3			
>3			

Carbohydrate antigen (CA) 19-9			
Median, U/mL			
Range, U/mL			
Normal (0-35 U/mL), n (%)			
ULN to <59x ULN, n (%)			
≥59x ULN, n (%)			
Previous therapy, n (%)			
Radiation therapy			
Chemotherapy			
Whipple procedure			
Biliary stent			

Figure 1. (A) Progression-free survival by investigator-assessment, (B) Progression-free survival by independent assessment, (C) Overall survival

Table 2. Progression-free survival and overall survival in the intention-to-treat population

Efficacy variable	Pembrolizumab n = x	Pembrolizumab + Paricalcitol n = x	Hazard ratio or Response-rate ratio (95% CI)	P value
Progression-free survival by investigator-assessment				
RECIST 1.1				
Rate of progression-free survival, % (95% CI)				
6 mo				
12 mo				
Median progression-free survival, mo (95% CI)				
Progression-free survival by independent assessment				

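### The tumour profiling behind two secondary endpoints has no feature list, significance level or error-rate control, and the SAP's reason for not adjusting cannot cover features that are not listed

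*Protocol*

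**What the plan says.** Protocol 3.5 makes mutational landscapes, transcriptional programs and cellular VDR targets secondary endpoints. Two analysis sections, both numbered 8.3.5.3, cover them.

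- **Mutational landscape and transcriptional programs.** The unit of analysis is an unlisted set: "The change in the biomarkers in the pre- versus 6-week biopsies will be estimated for each patient". Then: "A two-sample t test will be used to compare the continuous changes between the two treatment arms". A Wilcoxon rank sum test replaces the t test if the changes are not normal, and a regression adjusted for baseline is a sensitivity analysis.
- **Cellular VDR targets.** "Analysis of the specified cellular VDR targets will be assessed using the change in the pre-versus 9-week biopsies". The methods are carried over: "A two-sample t test or Wilcoxon Rank Sum Test, and a sensitivity analysis using linear regression will be performed as outlined previously".

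Protocol 6.1.2.8 describes the assays: "Bulk and single-cell analysis of mutational profiles, transcriptional profiles, and epigenetic states within tumors, including analysis of sorted tumor cell nuclei". For VDR it names VDR itself, CYP24A1, IL6, CXCL1, CSF2 and CXCLR. CYP24A1 and the four inflammatory genes are introduced by 'e.g.'. Neither document gives a complete target list.

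On multiplicity, SAP 7.2 says: "Since all primary and secondary endpoints are pre-specified, there will be no adjustment for multiple comparisons". The SAP is titled for clinical endpoints, and its secondary objectives are toxicity and overall survival only.

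**The concern.** A two-group test of change is a complete plan for one biomarker. For a profiling assay it leaves open how many tests there are, at what level each is judged, and how a reader should weigh the hits.

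The SAP's reason does not fill the gap. Naming an endpoint in advance prevents selection among endpoints. It does not limit false positives among many features inside one endpoint, and here the features are not named in advance. Protocol 3.2 adds to the uncertainty: objective 4 is to identify VDR targets, which is discovery language, while the analysis section speaks of specified ones.

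At stake is the trial's mechanistic conclusion (secondary objectives 3 and 4), drawn from at most 12 optional biopsy pairs per arm. The exploratory imaging plan in Appendix 7 does foresee holding back results from small groups so as not to overstate them. These higher-ranked endpoints have no such guard.

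**Working it through.** **The plan's own figures.** None is given for the biomarker endpoints. The only power figures, 90% (Pearson) and 89% (Miettinen-Nurminen) in 8.2, concern the primary endpoint. Exact enumeration with 12 per arm and 8% versus 58% gives 90.3% and 89.0%, so they reproduce, but they do not bear on this point.

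**Inputs.**
- Level per test: not stated for these analyses. Two-sided 0.05 is assumed. Appendix 7 uses that level, but only for imaging.
- Number of features m: not stated. 1,000 to 20,000 is assumed for untargeted profiling; 6 is the count of genes named in 6.1.2.8.
- Pairs per arm: at most 12 (SAP section 4). Biopsies are optional (6.1.2.8), so 4 to 12 is examined.

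**Step 1. Expected false positives when nothing changes** = m × 0.05. This needs no independence.
- m = 1,000: 50
- m = 20,000: 1,000

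**Step 2. Chance of at least one false hit in a short list** = 1 − 0.95^m, if independent.
- m = 6: 1 − 0.95^6 = 0.265, about 26%
- m = 10: 40%; m = 20: 64%

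For six genes, perfect correlation would lower the figure to 5%, and under any dependence it cannot exceed 6 × 0.05 = 30%.

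**Step 3. Share of hits that are false** = 0.05(1 − π) / [0.05(1 − π) + power × π], where π is the share of features that truly change (assumed). With 6 pairs per arm and a standardized effect of 1.5 (both assumed), power is 65%.
- π = 1%: 0.0495 / (0.0495 + 0.0065) = 88%
- π = 5%: 0.0475 / (0.0475 + 0.0325) = 59%
- π = 10%: 41%; π = 20%: 24%; π = 50%: 7%

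The share passes one half only when π is below 0.05 / (0.05 + 0.65) = 7%. Over 4 to 12 pairs and effects of 1.0 to 2.0, this break-even runs from about 5% to 18%.

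**Step 4. What control costs in power** (effect 1.5, Bonferroni as the harshest case).

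| Pairs per arm | Unadjusted | 10 tests | 20,000 tests |
|---|---|---|---|
| 12 | 94% | 70% | 3% |
| 6 | 65% | 24% | under 0.1% |

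Holm is never less powerful than Bonferroni, so a short list remains workable if most patients give paired biopsies. The last column shows why false discovery rate control, not family-wise control, suits the untargeted part.

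**The case against.** Several objections are fair.

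- **The feature count is assumed.** The documents do not say that profiling is genome-wide or that features are tested one at a time, and transcriptional programs could be a few summary scores. True, but no score is defined, and a t or Wilcoxon test of change is the only method offered. The plan should settle this.
- **A reader might infer that most reported VDR targets would be false.** The documents do not support that. VDR targets are a separate endpoint, described as a specified set and illustrated by a few candidate genes. Step 3 shows that a false majority needs few features to be truly changed, which is plausible for an untargeted screen but not for known VDR-responsive genes.
- **SAP 7.2 may not govern the biomarkers.** Given the title and objectives, that is the more natural reading. The gap then widens, since no rule applies to them.
- **A reader might infer that bulk RNA results would be artefacts of cell mix.** Section 1.3 does report more CD3 infiltration with paricalcitol, but such a shift would itself be a treatment effect. Section 6.1.2.8 also plans single-cell and tissue-based assays of the cell populations. Adjusting the main analysis for a fraction that treatment may alter risks removing the effect sought.
- **A reader might infer that freezing medium biases the comparison.** Section 6.1.2.8 says "snap frozen and Bambanker™ frozen tissue may be used interchangeably where technically feasible", but only if tissue runs short. Between randomised, blinded arms, mismatch mainly adds noise. It would bias the comparison only if mismatch differed by arm, and nothing suggests that.

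**Conclusion.** The concern holds in a limited form and should be fixed. For the mutational and transcriptional endpoints the plan has no feature list, level or error-rate control, and either reading of the SAP leaves them uncontrolled. For VDR targets the set is called specified, but only examples appear.

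If nothing changes, an untargeted screen yields about 50 false hits per 1,000 features, and the six example genes carry about a 26% chance of at least one if independent. Both figures assume 0.05 per test, and the feature counts of the screen are also assumed. That most VDR targets would be false, or that freezing medium would bias the arms, is not shown. The primary endpoint is unaffected.

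**What to change.** 1. **Protocol 8.3.5.3, Cellular VDR targets:** fix the list of targets before unblinding, starting from the genes named in 6.1.2.8. Test it as one family with Holm adjustment at a stated level.
2. **Protocol 8.3.5.3, Mutational Landscape and Transcriptional Programs:** analyse all other transcripts, mutations and epigenetic features with moderated statistics and Benjamini-Hochberg false discovery rate control (for example 10%). Report q-values and label these results hypothesis-generating.
3. **SAP 7.2:** state that the no-adjustment sentence covers only the SAP's clinical endpoints (primary, toxicity and overall survival), not the biomarker endpoints.

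Any adjustment of bulk RNA changes for cell fractions from the same biopsy should be at most a sensitivity analysis, reported beside the unadjusted result.

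The same edit should reconcile the on-treatment biopsy time: the mutational and transcriptional section says 6 weeks, while 6.1.2.8 and the VDR-target section say 9.

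The cost is protocol and SAP wording, standard software and fewer nominally significant features. No extra tissue or patients are needed.
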